Title: Researching Resiliency in Stressful Experiences (RISE) Program for Men Leaving Incarceration

NCT #: NCT04785677

Date: 4/14/2020

Study Summary

Study Title	Multisite Randomized Controlled Trial of Comprehensive Trauma Informed Reentry Services for Moderate to High Risk Youth Releasing From State Prisons
Study Design	1:1 Randomized Control Trial
Primary Objective	Determine whether the TARGET program helps young men released from prison improve their mechanisms of change.
Secondary Objective(s)	Determine whether the TARGET program helps young men released from prison improve their community stability and decrease their odds of recidivating.
Research Intervention(s)	Trauma Affect Regulation: Guide for Education and Therapy (TARGET)
Study Population	Incarcerated men aged 18-35 who have experienced at least one traumatic event in their lifetime. .
Sample Size	400
Study Duration for individual participants	Up to 18 Months
Study Specific Abbreviations/ Definitions	Lifetime Traumatic Events (LTE), Trauma Affect Regulation: Guide for Education and Therapy (TARGET), Department of Corrections (DOC).

1.0 Objectives*

1.1 The purpose of this study is to evaluate the impact of a comprehensive trauma-based reentry program for moderate- to high-risk young incarcerated males between the ages of 18-35 on post-release outcomes. We will assess changes in key mechanisms of change (i.e. mediators) as well as post-release outcomes. The key mechanisms of change include: trauma symptoms (PTSD, depression, anxiety, and substance abuse), coping, impulsivity, and aggression. Post-release outcomes include community stability (i.e., housing and employment), and recidivism (i.e., re-arrest and re-incarceration for technical violation or new crime; time to re-incarceration).

1.2 Research Questions

- RQ1: Does a comprehensive trauma-based reentry program improve key mechanisms of change for moderate- to high-risk young incarcerated males?
- RQ2: Does a comprehensive trauma-based reentry program improve community stability for moderate- to high-risk young incarcerated males?
- RQ3: Does a comprehensive trauma-based reentry program decrease rates of recidivism for moderate- to high-risk young incarcerated males?

2.0 Background*

2.1 More than 2.2 million young males have some contact with the criminal justice system each year; nearly 50% of Black males and 40% of White males are arrested for non-traffic related crimes by age 23.¹ Close to 200,000 young males are currently incarcerated in state and federal prisons across the nation; just under 20% of the total state prisoner population are young males at time of release.^{2,3} Younger age at prison intake and release are potent predictors of increased risk level; thus, young males are disproportionately identified as moderate- or high-risk for recidivism on standardized assessments. After release from incarceration, young males have the highest recidivism rate of any age group - 76% are rearrested for a new crime within 3 years.⁴ In a recent recidivism analysis, 90% of young men at time of release were re-arrested within nine years, with 52% of arrests occurring within the first year.⁵

The existence of an inverse, curvilinear relationship between age and both arrest and incarceration is treated as an “iconic fact” in the field of criminology,⁶ a fact which suggests that young males essentially “grow up” and grow out of committing crime.^{7,8} However, current recidivism rates among this group in particular indicate that some critical facet of young males’ experience is missing from existing correctional interventions.⁹ One potential driver of young males’ recidivism may be the unaddressed mental health symptoms and substance abuse which result from extremely high prevalence rates of lifetime traumatic experiences (LTEs).¹⁰⁻¹³ According to the American Psychiatric Association (2013), LTEs include direct personal experiences of victimization, threat or experience of serious injury, threat of death, learning of a serious injury

or death occurring to a loved one, or witnessing an event that involves death or serious injury/threat to another person in childhood, adolescence, or adulthood.

Across samples and study design, 62-98% of incarcerated males report at least one LTE (prior to incarceration)¹⁴⁻¹⁶ compared to 22-47% of men who have never experienced incarceration.^{17,18} Specifically, 58% of incarcerated males report physical abuse and 17% report sexual abuse in childhood - 2-3 times the estimated prevalence among males in community-based samples.¹⁹⁻²¹ Further, while discussions about LTEs typically center on the experiences of women and girls, incarcerated and formerly incarcerated males and females report equally high numbers of LTEs, although the nature of LTEs differ between the genders. Although incarcerated females report 2.5-4 times the rate of sexual abuse/assault as incarcerated males, incarcerated males report witnessing extreme harm to others at nearly double the rate as incarcerated females (60% vs. 34.8%).²² Incarcerated males also report interpersonal nonsexual trauma in adolescence at nearly twice the rate as incarcerated females (63.2% vs. 34.8%).²²

Addressing LTEs among incarcerated males is important because more than 95% of those who are incarcerated are eventually released²³ and trauma symptoms and risks for recidivism are correlated. Trauma symptoms include increased sensitivity to stress, high levels of negative emotionality, sensation seeking (i.e., pursuing risky, stimulating experiences),^{24,25} aggression, impulsivity, dissociation, impaired ability to adequately assess risk, and unrealistic expectations of interpersonal relationships.²⁶⁻²⁸ Rates of posttraumatic stress disorder (PTSD) are higher among males with incarceration histories (21%) when compared to both males in the general population (4%-5%) and male veterans (7%)^{16,21,29,30}; incarcerated males with substance use disorders are 80% more likely to have experienced two or more LTEs³¹ including previous physical or sexual assault.¹² These individuals struggle to remain abstinent from drugs and alcohol after release from incarceration^{12,32,33} and are more likely to be re-arrested when compared to their non-victimized peers.^{10,34,35}

Moreover, trauma symptoms predict violent and nonviolent criminal behavior^{13,36} and formerly incarcerated males who have experienced LTEs are significantly more likely to have used violence prior to their incarceration and have a higher risk of engaging in violence after release when compared to their non-victimized peers.^{16,37-39} For young incarcerated males, frequent victimization is associated with onset of aggression early in life.¹⁰ Indeed, incarceration itself may exacerbate symptoms associated with untreated LTEs.^{11,40,41} For incarcerated individuals, the number of LTEs is highly correlated with the number of incarcerations. Experiences of trauma increase the odds of arrest, incarceration, and recidivism, which, in turn, contributes to a higher likelihood of additional trauma.^{42,43}

A substantial body of neuroscientific and psychological research identifies why intervening with young offenders is particularly important. The adolescent and young adult (ages 10-25) brain is actively developing, growing at a rate comparable to that of infancy.⁴⁴ The young brain is engaged in a highly sensitive dual process of pruning and myelination to maximize efficiency and integration. This process of neural pathway development is responsive to and

dependent on the environment, making young people particularly sensitive to LTEs.^{44,45} The frontal lobe develops through age 25 and controls all executive functions including memory, judgment, impulse control, and planning, often resulting in impulsivity and risk-taking among young adults. Further, the hypothalamic-pituitary-adrenal (HPA) axis, a central part of the stress-response system, undergoes significant development during this time; young adults release greater amounts of the stress hormone, cortisol, when faced with highly stressful challenges and demonstrate higher levels of activity in the amygdala, part of the brain responsible for responding to threat.⁴⁶ Due to the vulnerability of the developing brain and stress response systems, witnessing or experiencing violence during this time decreases impulse control and retards growth toward future orientation which underscores the urgent need to intervene at this particularly malleable developmental stage.⁴⁷

Gaps in Current Knowledge. Despite incarcerated males' extremely high rates of trauma exposure, research to date has focused nearly exclusively on providing trauma treatment to incarcerated females. Only 28 states provide any correctional-based trauma treatment⁸¹. Of those states, 13 offer trauma treatment to men, meaning that 75% of incarcerated males have no access to any interventions designed to reduce the impact of LTEs, despite males and females reporting nearly equivalent rates of trauma exposure, albeit different types of LTEs. Further, the existing evidence supporting trauma-based correctional interventions is limited by a lack of randomized controlled trials (RCTs) conducted with incarcerated or formerly incarcerated males. Findings from a recent meta-analysis⁴⁸ suggest that there are gender differences in response to psychological interventions, with women reporting greater reductions in mental health symptom burden when compared to men post-intervention and at follow-up. This strongly suggests that intervention adaptations and tailored content need to be developed to more effectively respond to the trauma treatment needs of men. Finally, nearly all trauma-based correctional interventions are delivered during custody; only one published study provides any treatment post-release.⁴⁹ Therefore, the unique complexities of the reentry period, and the changing needs of individuals as they leave incarceration and return to their communities are not integrated into existing trauma-based interventions. This gap means that little is known about how to implement trauma treatment for young males during reentry, when stress is heightened, and they must manage housing instability while searching for employment. Interventions that span prison-to-community are essential to improving well-being and reducing recidivism among this population.

Although trauma-based interventions are rarely delivered to this population, cognitive-behavioral group-based interventions have been successfully implemented among samples of racially diverse criminal justice-involved or at-risk young males.⁵⁰⁻⁵² In a recent systematic review of individual and group-based psychological interventions designed to address both criminological (crime specific) and psychosocial risks⁵³, these approaches were identified as especially potent for reducing risk and improving well-being among the highest-risk, highest-need, hardest-to-engage offenders. Further, robust

associations between LTEs and both homelessness and unemployment have been noted for a range of high-risk populations. For example, LTEs have been significantly associated with increased days of homelessness ($\beta = .18$), poorer physical health ($\beta = -.23$), and drug use ($\beta = .22$) among homeless veterans.⁵⁴ Additionally, homeless patients with co-occurring mental health and substance use disorders were significantly more likely to attend substance abuse treatment when compared to those diagnosed only with a substance use disorder.⁵⁵ Individuals in a nationally representative sample who experienced childhood LTEs were twice as likely to be unemployed (OR=2.0) compared to those with no history of LTEs. Unemployment rates were amplified for those who experienced childhood physical abuse (OR=2.4) and multiple forms of trauma (OR=2.9).⁵⁶

Interventions which begin during custody and extend in the community after individuals have released from incarceration have shown the strongest short- and long-term effects.⁵⁷⁻⁶¹ Adding a community aftercare component to prison-based substance abuse treatment positively impacts recidivism, with RCTs demonstrating a 48% reduction in 3-year recidivism for individuals who received both in-prison treatment and aftercare (27%) compared to individuals who only received in-prison treatment (75%).⁶² Including post-release services extends the protective benefits of in-prison treatment, increasing sobriety and decreasing re-arrest.

We propose a comprehensive trauma-based reentry program for moderate- to high-risk young incarcerated males between the ages of 18-35 on post-release outcomes. Combining evidence-informed trauma treatment for LTEs with a holistic reentry approach focused on community stabilization factors will catalyze the reduction of trauma symptoms, impulsivity, and aggression, while increasing coping, housing stability, and employment – all factors critical to reducing recidivism. Beginning the intervention during custody allows for the development of a therapeutic and trusting relationship between group members and clinicians, increasing post-release treatment retention. Building on the reentry planning work pre-release, post-release groups will focus on the tangible needs of housing and employment, while simultaneously addressing the after-effects of LTEs as they arise in real time during this critical phase of brain development and reentry phase transition. Thus, we propose that participation in comprehensive trauma-based reentry program will increase housing stability and employment, based on the established relationship between trauma symptoms, coping, impulsivity, aggression, housing, and employment.⁵³⁻⁶² Decreased trauma symptoms, impulsivity, and aggression paired with increased coping and community stability will reduce recidivism among this sample of moderate- to high-risk young males as they leave incarceration and return to their communities.

3.0 Study Endpoints*

3.1 Comprehensive trauma-based reentry program group members will show improvements in key mechanisms of change compared to TAU control group members.

3.2 Comprehensive trauma-based reentry program group members will have increased community stability compared to TAU control group members.

3.3 Hypothesis 3: Comprehensive trauma-based reentry program group members will have lower rates of recidivism and those who do recidivate will spend more days in the community prior to recidivism compared to TAU control group.

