Power analysis. To determine the sample size, we conducted an a priori power analysis with the software program G*Power. We conducted the power analysis to make sure we would be able to detect differential effects on key mechanisms of change and community stability between participants allocated into the two study conditions. We powered the study based on conducting multivariate analysis using ANCOVA. We used a small effect size estimate - Cohen's d of .15 - based on guidance and data from the Clinician Administered PTSD Scale on a similar population.⁶⁷ Being able to detect small effects is important as we may find minimal difference between group members. Using an alpha of .05 and powered at a .80 level across two groups with up to seven covariates, a sample of 352 would allow us to detect small effects. Thus, a targeted sample size of 400 provides statistical power greater than .80, giving us strong confidence that we will be able to detect even small difference between study conditions.

Recidivism. Survival analysis will be conducted to analyze time-to-event on recidivism outcomes (i.e., time to arrest and time to incarceration). Participants without the occurrence of the events will be censored at their last known event-free time point. Survival curves will be constructed using Kaplan-Meier estimates. Using the Kaplan-Meier curve allows us to derive the median, or that time at which 50% of cases of the event of interest has occurred, and the mean (i.e. the average time it took for the event to occur). Although there are several methods available to analyze time-to-event curves, the proposed study uses a Cox proportional hazard model which is a regression method for survival data and has been used in previous criminal justice-related studies. The Cox model allows for the identification of differences in survival rate due to study condition and prognostic factors, such as covariates. Further, the Cox model provides an estimate of the hazard ratio and its confidence interval. There are two underlying assumptions of the Cox proportional hazard model: (1) the hazard ratios of two people are independent of time and (2)

are valid only for time independent covariates. For the current study, results will be displayed for comparison of survival distributions for three years post-release.

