Power Analysis. The Bureau of Justice Statistics (BJS) 2005-2014 data show that 76.5% of prisoners age 24 or younger released in 2005 were arrested within three years of release. Specifically, 51.8% were arrested within the first year, an additional 17% in the second year, and an additional 7.7% in the third year. Our goal is to reduce recidivism by 28% over three years. Using these data and the method described by Collett (2003, pp. 299-312), we calculate that the hazard ratio of recidivism for this study at 1.39, meaning that members of the control group will recidivate 39% faster than participants receiving the targeted treatment. Using the same BJS data, we calculated the median survival time (pre-recidivism) for members of the control group at 17.28 months. The median survival time suggests that 50% of the control group will recidivate by 17.28 months after release from incarceration. These data provided the basis for the power calculation. The power analysis was conducted using PS software.⁷⁸ Results show that for a study with 200 experimental participants and 200 control participants, a hazard ratio of recidivism of 1.39, and a median survival time for the control group of 17.28 months, we will be able to reject the null hypothesis that the treated and control survival curves are equal with a probability (power) of .810. The Type I error probability associated with this test of this null hypothesis is 0.05. Therefore, the study will have adequate statistical power.

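### The second clause of Hypothesis 3 compares days to recidivism only among men who recidivate, a contrast that randomisation does not protect and that no SAP analysis matches

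*Protocol*

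**What the plan says.** Protocol section 3.0 (Study Endpoints), item 3.3, has two clauses. The first is that program members "will have lower rates of recidivism" than controls; this concerns everyone randomised. The second is that "those who do recidivate will spend more days in the community prior to recidivism"; this concerns only the men who have the event.

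The SAP's Recidivism paragraph plans a time-to-event analysis of arrest and incarceration. On men without the event it says: "Participants without the occurrence of the events will be censored at their last known event-free time point". It then says "Using the Kaplan-Meier curve allows us to derive the median" and, from the same curve, "the mean (i.e. the average time it took for the event to occur". For the comparison of arms, "the proposed study uses a Cox proportional hazard model", giving a hazard ratio with a confidence interval. The horizon is set by the statement that "results will be displayed for comparison of survival distributions for three years post-release". No test in the SAP is confined to men who recidivate.

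**The concern.** Whether a man recidivates is decided after randomisation, and the program is designed to change it. The first clause of 3.3 predicts fewer recidivists in the program arm, so on the protocol's own reasoning the two recidivist groups will differ in composition. A difference in their mean times mixes any delay of events with a change in who has an event at all. If the program prevents mainly later events, the program men who remain in the comparison are those with early events, and their average time falls.

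At stake is how this clause would be reported. An analyst who took 3.3 literally would compare mean days among recidivists. That result could understate a real benefit or point the wrong way, and it would sit beside a Cox result that answers another question.

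A smaller point concerns the SAP's mean. A Kaplan-Meier mean is the area under the curve. If the curve has not reached zero when follow-up ends, the area beyond that time is unknown, and the SAP names no time at which to stop.

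**Working it through.** **Inputs.** From the SAP's recidivism power paragraph: control median 17.28 months; 200 men per arm; alpha 0.05 (two-sided assumed); stated power .810; and "we calculate that the hazard ratio of recidivism for this study at 1.39", control relative to program. From the Recidivism paragraph: a three-year horizon, τ = 36 months. Assumed: exponential times.

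**1. The plan's own figure.** Hazards per month are control ln 2 / 17.28 = 0.04011 and program 0.04011 / 1.39 = 0.02886. Power is Φ(½ √d · ln 1.39 − 1.96), where d is the expected number of events.
- Every man followed exactly 36 months: d = 282, power 0.790.
- The protocol's 18-month enrolment plus 36 months of follow-up: d = 311, power 0.828.
- 18 months of enrolment plus 30 months of follow-up: d = 292, power 0.803.

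The stated .810 lies within this range. The SAP does not give its accrual and follow-up inputs, so an exact match cannot be expected. These inputs are a fair basis for the next step.

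**2. Event-free at 36 months.** S(36) = exp(−36 × hazard): control 0.236, program 0.354.

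**3. All men: restricted mean time to 36 months.** RMST = (1 − S(36)) / hazard.
- Control: 0.764 / 0.04011 = 19.05 months.
- Program: 0.646 / 0.02886 = 22.39 months.
- Difference: +3.34 months (about 102 days).

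**4. Recidivists only.** Mean = (RMST − 36 · S(36)) / (1 − S(36)).
- Control: (19.05 − 8.49) / 0.764 = 13.81 months.
- Program: (22.39 − 12.74) / 0.646 = 14.94 months.
- Difference: +1.13 months (about 34 days), which is 34% of the all-men difference.

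**5. Timing of the effect.** The control arm is unchanged. The program hazard is piecewise constant, with RMST summed over the pieces and the formula of step 4 applied. Only the first row uses the SAP's effect; the others are assumptions made to show the range.

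| Program effect | Event-free at 36 months | Recidivists-only difference | All-men RMST difference |
|---|---|---|---|
| Hazard ratio 1/1.39 throughout | 35% | +1.13 | +3.34 |
| Hazard halved in year 1 only | 30% | +3.30 | +3.73 |
| Hazard × 0.6 in year 1 only | 29% | +2.53 | +2.92 |
| No effect for 6 months, then 1/1.39 | 33% | −0.06 | +2.07 |
| No effect for 12 months, then 1/1.39 | 31% | −0.65 | +1.18 |
| No effect for 12 months, then halved | 38% | −1.60 | +2.25 |

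For the last row, S(12) = 0.618 and S(36) = 0.618 × exp(−24 × 0.02006) = 0.382. RMST = 0.382 / 0.04011 + 0.618 × 0.382 / 0.02006 = 21.30 months. The recidivists-only mean is (21.30 − 13.75) / 0.618 = 12.21 months, against 13.81 in control.

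**6. Curve shape.** The yearly arrest rates quoted in the SAP (51.8%, 17%, 7.7%) give a steeper early curve. With hazards constant within each year and the hazard ratio 1.39, the differences are +1.01 months among recidivists and +3.66 in all men, so the picture is similar. With a year-1-only benefit on that curve (hazard × 0.5 or 0.6), the recidivists-only difference falls short by 28–30%.

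**7. Sampling error.** In 4,000 simulated trials at the SAP's inputs, the recidivists-only difference had the wrong sign in 17%. A t-test on it had about 15% power.

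**The case against.** The strongest reply is that nobody plans to run the recidivists-only comparison. The only comparative test named for recidivism is the Cox model on all men, the power calculation concerns equality of the survival curves, and the protocol elsewhere lists time to re-incarceration without any such condition. On this view 3.3 is one loosely worded clause. Most of that stands: the planned analysis is sound, and the fault lies in the stated hypothesis and its mismatch with the SAP. But the clause appears under Study Endpoints, it has no matching analysis, and read literally it calls for a non-randomised contrast.

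Three stronger readings are tempting, and the documents do not support them.

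- *The SAP's mean is also confined to recidivists.* Its gloss is loose, but the mean is derived from the Kaplan-Meier curve, in which event-free men are censored and so included. Only the missing restriction time is at fault.
- *The recidivists-only contrast always loses about two thirds of the benefit.* That is the result for a constant hazard ratio of 1.39 at 36 months. With the SAP median and a benefit confined to year 1, the shortfall is about 12–13%.
- *The trial would report harm.* Reversal in expectation needs a delayed effect, which the documents do not state. Even then the planned analysis would show benefit. In 400 simulated trials with the hazard halved only after month 12, the Cox model favoured the program in 99.8% and was significant in 67%, with a median hazard ratio (program to control) of 0.74. The first clause of 3.3 would show re-arrest of 62% against 76%.

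**Conclusion.** The point holds as a defect in the wording of an endpoint, not as a flaw in the planned analysis. The second clause of 3.3 conditions on a post-randomisation event and has no counterpart in the SAP.

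Under the SAP's inputs, with exponential times and a constant hazard ratio, it would show +1.1 months where the restricted mean over all men differs by +3.3. The two are different estimands, and the distance between them depends on when the program acts: slight for an early benefit, and opposite in sign (−1.6 against +2.2 months) for the assumed late one. No single share should be quoted as the loss.

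The unrestricted Kaplan-Meier mean is a separate, smaller matter. With about 24% and 35% expected to be event-free at 36 months, it cannot be estimated from the data. The three-year window already in the SAP supplies the natural restriction time.

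**What to change.** In Protocol 3.3, replace the second clause with: *more days in the community before first recidivism over 36 months, in all randomised men*. Name the planned Cox model as its test, for arrest and for incarceration as the SAP already lists them.

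In the SAP's Recidivism paragraph, define the mean as the restricted mean to 36 months. Report the between-arm difference with its confidence interval beside the hazard ratio. This expresses the hypothesis in days and does not rely on proportional hazards. The Kaplan-Meier and Cox analyses stay as planned.

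The cost is a change of wording in both documents and one extra summary, using the recidivism data already to be collected annually for three years.
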